3.2 Objectives and related endpoints-phase II

Table 3-2 Objectives and related endpoints-phase II

	Objective	Endpoint
PHASE II		
Primary	Determine the Clinical Benefit Rate (CBR) at 24 weeks amongst patients receiving triple therapy with ribociclib + everolimus + exemestane, for advanced/metastatic HR+, HER2-negative breast cancer following progression on CDK 4/6 inhibitor.	Clinical Benefit Rate (CBR) defined as the proportion of patients with a complete (CR) or partial response (PR), or with stable disease (SD) at 24 weeks as per RECIST 1.1 or Non-CR Non-PD (NCRNPD) at week 24.
Secondary	To determine centrally assessed progression Free Survival (PFS) in HR+ HER2-negative advanced breast cancer.	Progression-free survival (PFS), defined as the time from date of treatment to the date of first documented progression or death due to any cause. If a

Objective	Endpoint
	subject has not had an event, PFS will be censored at the date of last adequate tumor assessment. Disease progression for primary efficacy endpoint derivation will be based on the central radiologist's tumor assessment.
To determine overall response rate (ORR)	Overall response rate (ORR) defined as the proportion of patients whose best overall response is either complete response (CR) or partial response (PR) according to RECIST 1.1.
To determine Overall Survival (OS)	This is defined as the time from treatment initiation with study treatment until death as a result of any cause.
To determine Duration of Overall Response (DOR)	Duration of Overall Response defined as the time between the initial response to the treatment with the combination of ribociclib+everolimus+ exemestane, and subsequent disease progression or recurrence.
To evaluate time to deterioration or ECOG performance status	Time to definitive deterioration of ECOG performance status from baseline.
To determine safety and tolerability	Adverse Events (AEs), serious AE (SAEs), changes in hematology and chemistry values, vital signs, dose interruptions, reductions and dose intensity.
To determine the PK profile of ribociclib and everolimus in the triplet combination	PK parameters including, but not limited to, AUC _{0-4h} , C _{trough} , C _{max} , accumulation ratio (Racc)

4 Study design

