***Note: Phase I does not require prior CDK 4/6 inhibitor exposure**

***Note: For patients who received prior CDK4/6 inhibition as part of a clinical trial, patients must be unblinded in order to verify that the patient did receive a CDK4/6 inhibitor.**

10. ECOG Performance Status 0 – 1.
11. Radiological evidence of recurrence or progression on or after the last therapy prior to starting study treatment.
12. Patients must have:
 - Measurable disease (based on RECIST 1.1): defined as at least one lesion that can be accurately measured in at least one dimension ≥ 20 mm with conventional imaging techniques or ≥ 10 mm with spiral CT or MRI,
OR
 - Evaluable disease: bone lesions- lytic or mixed (lytic + sclerotic) in the absence of measurable disease
13. Patient has adequate bone marrow and organ function as defined by the following LOCAL laboratory values at screening:

- Absolute neutrophil count $\geq 1.5 \times 10^9/L$.
 - Platelets $\geq 100 \times 10^9/L$.
 - Hemoglobin $\geq 9.0 \text{ g/dL}$.
 - Potassium, total calcium (corrected for serum albumin), magnesium and sodium within normal limits for the institution or corrected to within normal limits with supplements before first dose of study medication.
 - INR ≤ 1.5 or ≤ 2.5 while on anti-coagulant.
 - Estimated glomerular filtration rate (eGFR) $\geq 30 \text{ mL/min/1.73m}^2$ according to the Modification of Diet in Renal Disease (MDRD) formula
 - Serum creatinine $< 1.5 \text{ mg/dL}$ or creatinine clearance $\geq 50 \text{ mL/min}$.
 - Total bilirubin $< \text{ULN}$ except for patients with Gilbert's syndrome who may only be included if the total bilirubin is $\leq 3.0 \times \text{ULN}$ or direct bilirubin $\leq 1.5 \times \text{ULN}$.
 - Alanine aminotransferase (ALT) and aspartate transaminase (AST) $< 2.5 \times \text{ULN}$, except for patients with liver metastasis, who are only included if the AST is $< 5 \times \text{ULN}$.
14. Must be able to swallow ribociclib, everolimus and exemestane capsules/tablets.
15. Patients with metastatic disease are allowed to receive ≤ 28 days of endocrine therapy prior to starting study treatment.

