10.5.2 Secondary objective(s)

Progression-free survival (PFS), defined as the time from date of treatment to the date of first documented progression or death due to any cause.

PFS will be analyzed using the Kaplan-Meier Product-Limit method. Patients who do not progress will be censored at the last adequate assessment. Estimates of the 25th, median and 75th percentile of the PFS and their 95% confidence intervals will be provided, if applicable.

Overall response rate (ORR) defined as the proportion of patients whose best overall response is either complete response (CR) or partial response (PR) according to RECIST 1.1. ORR will be calculated based on FAS according to the IIT principle; however, patients with only non-measurable disease at baseline will be included in the numerator if they achieved a complete response. ORR will be summarized by frequency and percentage. Disease Control Rate (DCR) in Phase I will be summarized by prior CDK 4/6 inhibitor treatment status with accompanying 95% confidence intervals.

Overall survival (OS) is defined as the time from date of first treatment to the date of death due to any cause. If a patient is not known to have died, survival will be censored at the last date of contact. OS will also be summarized by Kaplan-Meier Product-Limit method.

Duration of Overall Response (DOR) applies only to patients whose best overall response is CR or PR according to RECIST 1.1. The start date is the date of first documented response (CR or PR) and the end date is the date defined as first documented progression or death due to underlying cancer. In other words, the start date should be determined using the time that the response was first determined and not using the time the response was confirmed. If a patient had not had an event, duration will be censored at the date of the last adequate tumor assessment. DOR will be listed and summarized by treatment arm.

ECOG performance scale as described in [Table 7-3](#) will be used to assess physical health of patients. An analysis of time to definitive deterioration of the ECOG PS by one category of the score from baseline will be performed. Deterioration is considered definitive if no improvements in ECOG PS status is observed at a subsequent time of measurement during treatment period following the time point where the deterioration is observed.

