14.2.26 Handling of patients with non-measurable disease only at baseline

It is possible that patients with only non-measurable disease present at baseline are entered into the study, either because of a protocol violation or by design (e.g. in Phase III studies with PFS as the primary endpoint). In such cases the handling of the response data requires special consideration with respect to inclusion in any analysis of endpoints based on the overall response evaluations.

It is recommended that any patients with only non-measurable disease at baseline should be included in the main (ITT) analysis of each of these endpoints.

Although the text of the definitions described in the previous sections primarily relates to patients with measurable disease at baseline, patients without measurable disease should also be incorporated in an appropriate manner. The overall response for patients with measurable disease is derived slightly differently according to Table 14-6.

Table 14-6 Overall lesion response at each assessment: patients with non-target disease only

Non-target lesions	New Lesions	Overall lesion response
CR	No	CR
Non-CR/Non-PD ¹	No	Non-CR/non-PD
UNK	No	UNK
PD	Yes or No	PD
Any	Yes	PD

¹ As defined in [Section 14.2.8](#).

In general, the **non-CR/non-PD response** for these patients is considered equivalent to an SD response in endpoint determination. In summary tables for best overall response patients with only non-measurable disease may be highlighted in an appropriate fashion e.g. in particular by displaying the specific numbers with the non-CR/non-PD category.

In considering how to incorporate data from these patients into the analysis the importance to each endpoint of being able to identify a PR and/or to determine the occurrence and timing of progression needs to be taken into account.

For ORR it is recommended that the main (ITT) analysis includes data from patients with only non-measurable disease at baseline, handling patients with a best response of CR as “responders” with respect to ORR and all other patients as “non-responders”.

For PFS, it is again recommended that the main ITT analyses on these endpoints include all patients with only non-measurable disease at baseline, with possible sensitivity analyses which exclude these particular patients. Endpoints such as PFS which are reliant on the determination and/or timing of progression can incorporate data from patients with only non-measurable disease.

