3.5.2.2 Phase II

- Clinical Benefit Rate (CBR):

Clinical Benefit Rate (CBR) is defined as the proportion of patients with a complete response (CR), partial response (PR), stable disease (SD) or Non-CR Non-PD (NCRNPD) at 24 weeks as per RECIST V1.1. Thus, any instance of CR, PR, SD or NCRNPD in the first 24 weeks of the treatment, without having an instance of progressive disease (PD) will be accounted for, while calculating CBR. The instances of unconfirmed CR and/or PR will also be accounted for, while calculating CBR.

Demonstration of significant Clinical Benefit Rate (CBR) will be based on this study with at least an 80% power to test the null hypothesis that the clinical benefit rate in 24 weeks is at least 10% or less with an alternative hypothesis that this rate is above 10%.

All the other patients will be counted as not having clinical benefit.

The study is designed to test the following statistical hypothesis:

$$H_0 : \text{CBR} \leq 10\% \text{ vs. } H_1 : \text{CBR} > 10\%$$

The null hypothesis will be rejected and successful clinical benefit will be demonstrated if the lower limit of the 95% confidence interval is greater than at least 0.10. Thus, if 8 or more patients show clinical benefit at 24 weeks then the null hypothesis will be rejected and significant clinical benefit will be demonstrated.

To show significant clinical benefit, currently at least ≥ 8 patients will have to achieve CBR at 24 weeks. But if the number of patients enrolled in the study is higher than the planned number of 33 patients (approximately 44 to 46), then the requirement for the number of patients to have achieved CBR will also increase (up to ≥ 10 patients).

CBR will be summarized by frequency and percentage together with the 95% confidence intervals. An exact binomial confidence interval (implemented using SAS procedure FREQ with EXACT statement for one-way tables) will be calculated [Clopper & Pearson, 1934].

CBR will be calculated based on FAS; however, patients with only non-measurable disease at baseline will be included in the numerator if they achieved a complete response.

For primary efficacy variable, the analysis time point is when all patients who are enrolled complete 24 weeks or discontinue from the study earlier. Phase 1 patients who had received the RP2D and are post CDK 4/6 completing 24 weeks or discontinue early will also be included in the final phase II analysis.

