3.7.2.1 ORR, DCR and CBR

- ORR:

Overall response rate (ORR) defined as the proportion of patients who's best overall response is either complete response (CR) or partial response (PR) according to RECIST 1.1. ORR will be calculated based on FAS; however, patients with only non-measurable disease at baseline will be included in the numerator if they achieved a complete response. ORR will be summarized by frequency and percentage. The exact 95% two-sided confidence interval will also be provided.

When examining overall response, patients with a best overall response assessment of unknown (UNK) will not be regarded as “responders” but may be included in the denominator for ORR calculation.

Best overall response for each patient will be listed and summarized on FAS.

- DCR:

Disease control rate (DCR) is the proportion of patients with a best overall response of CR or PR or SD. DCR will be calculated based on FAS; however, patients with only non-measurable disease at baseline will be included in the numerator if they achieved a complete response. DCR will be summarized by frequency and percentage. The exact 95% two-sided confidence interval will also be provided.

When examining disease control, patients with a best overall response assessment of unknown (UNK) will not be regarded as “responders” but may be included in the denominator for DCR calculation.

- CBR:

CBR is defined as the proportion of patients with a CR, PR, SD or NCRNPD as per RECIST V1.1 by week 24. Thus, any instance of CR, PR, SD or NCRNPD in the first 24 weeks of the treatment, without having an instance of PD will be accounted for, while calculating CBR. The instances of unconfirmed CR and/or PR will also be accounted for, while calculating CBR.

CBR will be calculated based on FAS; however, patients with only non-measurable disease at baseline will be included in the numerator if they achieved a complete response. CBR will be summarized by frequency and percentage together with the 95% confidence intervals. An exact binomial confidence interval (implemented using SAS procedure FREQ with EXACT statement for one-way tables) will be calculated [Clopper & Pearson, 1934].

When examining clinical benefit, patients with a best overall response assessment of unknown (UNK) will not be regarded as “responders” but may be included in the denominator for CBR calculation.

- **Phase II**

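### The SAP's primary CBR section counts non-CR/non-PD as clinical benefit, then applies an ORR clause that, as naturally read, denies it to the only patients who can have that response

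*SAP*

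**What the plan says.** **Definition of the endpoint.** SAP 3.5.2.2 defines CBR as the proportion of patients with CR, "partial response (PR), stable disease (SD) or Non-CR Non-PD (NCRNPD) at 24 weeks as per RECIST V1.1". It adds that any such instance in the first 24 weeks without progression counts. Protocol Table 3-2 agrees: CR or PR, "or with stable disease (SD) at 24 weeks as per RECIST 1.1 or Non-CR Non-PD (NCRNPD) at week 24".

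**The added clause.** Later in SAP 3.5.2.2, CBR is to be calculated on the full analysis set (FAS), with the qualification that "patients with only non-measurable disease at baseline will be included in the numerator if they achieved a complete response". SAP 3.7.2.1 repeats this for Phase I CBR ("CBR will be calculated based on FAS; however, patients with only non-measurable disease at baseline will be included in the numerator") and for DCR.

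**Where the clause stands in the protocol.** Protocol 10.5.2 attaches it to ORR: "ORR will be calculated based on FAS according to the IIT principle; however, patients with only non-measurable disease at baseline will be included", with CR as the condition for counting them. Appendix 2, section 14.2.26, gives the CR-only handling for ORR as well: "For ORR it is recommended that the main (ITT) analysis includes data from patients with only non-measurable disease at baseline", with CR as response and everything else as non-response. The same section says of a non-CR/non-PD result that it "for these patients is considered equivalent to an SD response in endpoint determination". The protocol's own primary CBR analysis (10.5.1) has no such clause.

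**Who is affected.** Protocol 5.2, criterion 12, admits patients with "bone lesions- lytic or mixed (lytic + sclerotic) in the absence of measurable disease".

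**Declared changes.** SAP section 5 lists none.

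**The concern.** The two statements in SAP 3.5.2.2 pull apart for one eligible subgroup. If CR is the condition for entering the numerator, a patient with lytic bone disease who is non-CR/non-PD through week 24 has clinical benefit under the definition and no clinical benefit under the clause. That patient would still be in the FAS denominator.

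Phase II success in each group rests on a fixed count: 8 patients, rising to 10 if 44 to 46 are enrolled. A few reclassified patients can therefore change a group's conclusion. Two programmers working from the same section could produce different primary results. The trial is open-label, so a choice of reading made after the data are seen would be hard to defend. If the restrictive rule is intended, it changes the protocol's primary endpoint without being declared.

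**Working it through.** **1. Which patients can be NCRNPD?** Protocol Table 14-6 (non-target disease only) allows four overall responses: CR, non-CR/non-PD, UNK and PD. Protocol Table 14-5 and SAP Table 3-3 (measurable disease) never yield non-CR/non-PD as an overall response. NCRNPD in the CBR definition can therefore only come from patients without measurable disease. A CR condition on those patients empties the category that the definition names.

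**2. Does the looser reading rescue the clause?** The clause says *if*, not *only if*, so it could be taken to exclude nobody. But CR already counts for every patient, so the sentence would then have no function, and its opening *however* would mark no contrast.

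**3. The plan's own figures.** Inputs: null rate 10%, alternative 30%, success at 8 or more of 33 (SAP section 4), 46 and 33 recruited (SAP section 4), at least 10 for the larger group (SAP 3.5.2.2). Exact binomial:

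- P(X ≥ 8 | n = 33, p = 0.10) = 0.0141; P(X ≥ 8 | 33, 0.30) = 0.818. The Clopper-Pearson 95% lower limit is 0.1109 at 8/33 and 0.0898 at 7/33, so 8 is the right cut-off.
- P(X ≥ 10 | 46, 0.10) = 0.0140; P(X ≥ 10 | 46, 0.30) = 0.921; lower limit at 10/46 is 0.1095.

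The 80% design power is reproduced for 8/33.

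**4. Effect of the restrictive reading.** Let f be the share of patients without measurable disease. The documents do not give f for this trial. The nearest figure is 22.0% with bone-only metastases in the first-line ribociclib plus letrozole trial (Protocol 1.2.2), a weak proxy. I show 10%, 22% and 30%.

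- Case A: true CBR 30% in everyone, no CR in the subgroup. Counted rate p = 0.30(1 − f) = 0.270, 0.234, 0.210.
- Case B: CBR in the subgroup half that of other patients, overall still 30%. p = (1 − f) × 0.30/(1 − 0.5f) = 0.284, 0.263, 0.247.
- Case C: as A, but 5% of the subgroup reach CR. p = 0.30(1 − f) + 0.05f = 0.275, 0.245, 0.225.

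| Power | f = 0 | f = 10% | f = 22% | f = 30% |
|---|---|---|---|---|
| ≥8/33, case A | 81.8% | 70.2% | 52.2% | 38.9% |
| ≥8/33, case B | 81.8% | 76.1% | 67.0% | 59.1% |
| ≥8/33, case C | 81.8% | 72.4% | 58.0% | 47.2% |
| ≥10/46, case A | 92.1% | 83.4% | 66.1% | 50.9% |
| ≥10/46, case B | 92.1% | 88.1% | 80.6% | 73.2% |
| ≥10/46, case C | 92.1% | 85.2% | 72.1% | 60.6% |

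In case A, power falls below 80% once f exceeds 1.8% for 8/33 and 12.8% for 10/46.

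**5. Type I error.** At a true CBR of 10%, with p = 0.10(1 − f), the rejection probability for 8/33 goes from 1.41% to 0.77%, 0.32% and 0.16%. For 10/46 it goes from 1.40% to 0.69%, 0.25% and 0.11%. The error is in the conservative direction.

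**The case against.** The strongest reply is that this is a misplaced ORR sentence rather than a contradiction. The operative rule in SAP 3.5.2.2 counts any NCRNPD without progression; SAP 3.3.1 refers to Protocol Appendix 2, which equates non-CR/non-PD with SD; and *None* in SAP section 5 suggests that no change was meant. The SAP sentence that counts all other patients as without benefit comes before the clause and most naturally refers to the definition, so it does not help the restrictive reading.

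That is a fair account of what was probably intended. It does not settle what the text says. Appendix 2 is general guidance, while the clause is specific to the primary analysis, and the benign reading works only by giving the sentence no effect.

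The objections to the size have more weight. Every power figure is conditional on the restrictive reading, an unknown share and assumed subgroup rates. Bone-only disease overstates the non-measurable share, because lytic or mixed lesions with a qualifying soft-tissue component are measurable (Protocol 14.2.4). The 1.8% threshold for 8/33 mostly reflects a thin margin: 81.8% against a target of 80%. Eligible Phase I patients treated at the RP2D also join the final analysis, so the analysed numbers will not be exactly 33 and 46.

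A last objection is that stating the SD equivalence for best overall response is unnecessary and could hide the separate display that Protocol 14.2.26 allows. It is needed. SAP 3.3.1.6 has no NCRNPD category, so taken literally these patients fall to UNK, and SAP 3.5.2.2 does not regard UNK as response for CBR. The separate display can be kept.

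**Conclusion.** The concern holds. SAP 3.5.2.2 does not give one rule for the primary numerator in an eligible subgroup, and its natural reading departs from the protocol endpoint without being declared. This follows from the text alone and needs no assumption.

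The numerical consequence is conditional. On the restrictive reading CBR is biased down and power is lost, by an amount set by a share that the documents do not report; the tabulated figures illustrate this and are not estimates for this trial. There is no inflation of type I error, and on the permissive reading there is no loss. Because the clause governs the primary test and that test is decided by a fixed count, it must be corrected before database lock.

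**What to change.** - Delete the clause on patients with only non-measurable disease from the CBR text (SAP 3.5.2.2 and 3.7.2.1) and the DCR text (3.7.2.1). Keep it for ORR.
- State in the SAP itself that NCRNPD is handled as SD for CBR, DCR and best overall response, in line with Protocol 14.2.26. NCRNPD may still be shown as its own row in the response tables.
- If the sponsor does intend a CR-only rule for these patients, declare it in SAP section 5 as a change from the protocol and restate the power.

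The cost is a few lines of SAP wording and one line of the derivation specification. No new data are needed.

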10.5 Objectives

10.5.1 Primary objectives

Phase I: The primary objective of this dose escalation part of the study is to estimate the MTD(s) and/or RP2D of ribociclib in combination with everolimus and exemestane in postmenopausal women with HR+ HER2- advanced breast cancer.

Phase II: The primary objective is to evaluate efficacy measured by Clinical benefit rate (CBR) at 24 weeks for the triple combination of ribociclib + everolimus + exemestane among patients with HR+HER2- advanced breast cancer following the progression of CDK 4/6 inhibitors.

Demonstration of significant Clinical Benefit Rate (CBR) will be based on this study with at least an 80% power to test the null hypothesis that the clinical benefit rate in 24 weeks is at least 10% or less with an alternative hypothesis that this rate is above 10%.

The Clinical benefit rate will be presented together with an exact 95% Clopper-Pearson confidence interval. The null hypothesis will be rejected and successful clinical benefit will be demonstrated if the lower limit of the 95% confidence interval is greater than at least 0.10. Thus, if 8 or more patients show clinical benefit at 24 weeks then the null hypothesis will be rejected and significant clinical benefit will be demonstrated. Primary efficacy analysis will be performed on the FAS. For primary efficacy variable, the analysis time point is when all patients who are enrolled complete 24 weeks or discontinue from the study earlier. Phase 1 patients who had received the RP2D and are post CDK 4/6 completing 24 weeks or discontinue early will also be included in the final phase II analysis.

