3.3.1.3 Non Responder

A patient will be called a non-responder if at any baseline visit, patient is assessed to have no response (unconfirmed response of CR/PR or response of SD, PD). A patient who discontinues for any reason before the data cut-off date of the CSR without a confirmed assessment of response will be considered a non-responder. Patients with unknown or missing response, or who are treated in the study but provide no information on response at the end of treatment will also be treated as non-responders.

The non-responders will be included in the denominator while calculating percentages.

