When examining clinical benefit, patients with a best overall response assessment of unknown (UNK) will not be regarded as “responders” but may be included in the denominator for CBR calculation.

For the primary analysis, CBR will be assessed based on the centrally assessed tumor responses provided by the Investigator according to RECIST Version 1.1. Additionally, above analysis will be repeated for CBR based on the locally assessed tumor response using full analysis set. Analysis will also be performed using per protocol analysis set, as appropriate.

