3.7.2.2 PFS, ORR, OS and DOR

- PFS:

Progression-free survival (PFS) is defined as the time from date of treatment to the date of first documented progression or death due to any cause. For PFS, a patient who didn't have the event at the date the analysis data cut-off will be censored at the time of the last adequate assessment, prior to data cut-off. PFS will be assessed based on the responses provided by the Investigator on centrally assessed data. The PFS will be analyzed using FAS.

PFS will be analyzed using the Kaplan-Meier Product-Limit method. Estimates of the 25th, median and 75th percentile of the PFS and their 95% confidence intervals will be provided, if applicable. Additionally, above analysis will be repeated on the locally assessed tumor response. Analysis will also be performed using per protocol analysis set, as appropriate.

- ORR:

Overall response rate (ORR) defined as the proportion of patients who's best overall response is either complete response (CR) or partial response (PR) according to RECIST 1.1. ORR will be calculated based on FAS; however, patients with only non-measurable disease at baseline will be included in the numerator if they achieved a complete response. ORR will be summarized by frequency and percentage. The exact 95% two-sided confidence interval will also be provided.

When examining overall response, patients with a best overall response assessment of unknown (UNK) will not be regarded as "responders" but may be included in the denominator for ORR calculation.

Best overall response for each patient will be listed and summarized on FAS.

- OS:

Overall survival (OS) is defined as the time from date of first treatment to the date of death due to any cause. If a patient is not known to have died, survival will be censored at the last date of contact.

OS will also be summarized by Kaplan-Meier Product-Limit method based on FAS. Estimates of the 25th, median and 75th percentile of the PFS and their 95% confidence intervals will be provided, if applicable.

- DOR:

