3.15 Interim analysis

No formal interim analysis is planned. One interim statistical analysis will be done after completing Phase I part of the study. The final analysis will be after completing Phase II of the study.

4 Sample size calculation

Phase I: In the phase I of the study, there will be 3-6 patients per dose level cohort (for a total of 3 cohorts). A RP2D will be based on safety profile of the dose escalation (cohort A&B) and the dose de-escalation (cohort C). RP2D will be defined as the optimal dose level at which 33%

or less experience DLTs. Thus, including confirmation, at least 3-6 patients will be required for Phase I for each cohort.

Phase II: The sample size is based on an exact test for single proportion to test the null hypothesis $H_0: p \leq 0.10$ where p is the clinical benefit rate in 24 weeks. If the true rate is $p \geq 30\%$, then with one-sided alpha level of 0.05% and a power of 80%, a minimum of approximately 60 (30 per group) evaluable patients are required for the study.

Including dropout rate of 10%, to get 60 evaluable patients, a total of approximately 66 patients (33 patients per group) will be enrolled for the phase 2 of the study for each group (group 1 and group 2). Thus, if fewer than 8 patients show clinical benefit at 24 weeks out of 33 patients within each group then the study will not show significant clinical benefit. Thus, approximately at least 66 patients (33 patients per group (group 1&2)) will be required to be enrolled for the Phase II of the study.

So far 46 patients for group 1 and 33 patients for group 2 are recruited for phase 2.

5 Change to protocol specified analyses

None

6 Appendix

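### One sentence in SAP 3.5.2.2 makes it optional to keep patients with unknown response in the CBR denominator, which the rest of the plan makes mandatory; if followed, it could let a group one patient short pass the confidence-interval criterion

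*SAP*

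**What the plan says.** Four statements bear on who is in the denominator of the primary CBR.

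- Protocol 10.5.1: "Primary efficacy analysis will be performed on the FAS". SAP 3.5.2.2 likewise bases CBR on the FAS, and SAP Section 5 declares no change from the protocol's analyses.
- SAP 3.5.2.2, after defining benefit: "All the other patients will be counted as not having clinical benefit".
- SAP 3.3.1.3 treats patients with unknown or missing response as non-responders and adds: "The non-responders will be included in the denominator while calculating percentages".
- SAP 3.5.2.2, later in the same section, on patients with best overall response UNK: not responders, "but may be included in the denominator for CBR calculation".

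The optional clause recurs for ORR, DCR and CBR in SAP 3.7.2.1 (Phase I) and for Phase II ORR in SAP 3.7.2.2 ("but may be included in the denominator for ORR calculation"). SAP 3.5.3, where missing data for the primary endpoint would be handled, is marked not applicable.

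Success is stated in two ways in SAP 3.5.2.2. One is that the lower limit of the exact 95% interval exceeds 0.10. The other is a count: at least 8 patients per group, rising to as many as 10 if about 44 to 46 are enrolled.

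**The concern.** The first three statements fix the denominator; the fourth makes part of it discretionary. Its likely source is the generic response guidance in Protocol 14.2.17, which uses the same optional wording for ORR and DCR but ties it to which analysis population is used. The SAP carried over the option without that condition, although it had already fixed the population as the FAS.

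Patients with unknown response can never be in the numerator. Leaving them out can therefore only raise the rate and the lower limit on which the interval criterion depends. The study is open-label (Protocol 6.6.2), so a denominator left open in the text could be settled after the outcomes are known. The sentence is also the most specific one on unknown responses under CBR, so a programmer could reasonably follow it.

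**Working it through.** **Inputs.** Null rate 0.10 and the exact (Clopper-Pearson) 95% interval come from SAP 3.5.2.2. Recruited sizes of 46 (Group 1) and 33 (Group 2), and the 10% dropout allowance, come from SAP Section 4.

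**Formula.** For r patients with benefit out of n, the lower limit is the 2.5% quantile of a Beta(r, n − r + 1) distribution. The group passes if this exceeds 0.10.

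**The plan's own thresholds, full denominator.**
- n = 33: 8/33 gives 0.1109 (pass) and 7/33 gives 0.0898 (fail). Threshold 8, as stated.
- n = 46: 10/46 gives 0.1095 (pass) and 9/46 gives 0.0936 (fail). Threshold 10, as stated. It is also 10 at n = 44 and 45.

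The thresholds therefore follow from the two-sided 95% interval. The one-sided level printed as 0.05% in SAP Section 4 would, read literally, require 11 of 33 and 13 of 46.

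**Leaving out patients with unknown response, one patient short of the threshold.**

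| Group | Left out | r/n | Rate | Lower limit | Interval rule |
|---|---|---|---|---|---|
| 1 | 0 | 9/46 | 19.6% | 0.0936 | fail |
| 1 | 2 | 9/44 | 20.5% | 0.0980 | fail |
| 1 | 3 | 9/43 | 20.9% | 0.1004 | pass |
| 2 | 0 | 7/33 | 21.2% | 0.0898 | fail |
| 2 | 3 | 7/30 | 23.3% | 0.0993 | fail |
| 2 | 4 | 7/29 | 24.1% | 0.1030 | pass |

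**Two patients short.** The largest n that passes is 36 with r = 8 and 23 with r = 6. Rescuing 8/46 or 6/33 would therefore take 46 − 36 = 10 or 33 − 23 = 10 exclusions.

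**Count rule.** With 8 required at 33 and 10 at about 44 to 46 enrolled, 7 and 9 fail however many unknown responses are removed. The two success rules would then give different answers for the same group.

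**Error rate.** Suppose 4 of 33 or 3 of 46 unknown responses were always left out. At a true FAS rate of 10%, the chance of meeting the interval criterion would be P(X ≥ 7 | 33) = 0.0417 instead of P(X ≥ 8 | 33) = 0.0141, and P(X ≥ 9 | 46) = 0.0364 instead of P(X ≥ 10 | 46) = 0.0140. Both exceed the 0.025 implied by a two-sided 95% interval.

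**Dependence on final size.** Protocol 10.5.1 and SAP 3.5.2.2 add Phase I patients treated at the RP2D after a CDK 4/6 inhibitor; their number is not given. For assumed sizes from 33 to 54, the exclusions that rescue a group one short range from 1 (n = 37, 44 or 51) to 7 (n = 36, 43 or 50).

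**Dropout allowance.** If every dropout had an unknown response (an assumption), 10% would be 3.3 of 33 and 4.6 of 46, or about 3 and 5. Three are not enough in Group 2 (7/30 fails); five would be enough in Group 1.

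**The case against.** The strongest reply is that the plan already answers the question. SAP 3.3.1.3 names unknown and missing response and keeps these patients in the denominator. SAP 3.5.2.2 and Protocol 10.5.1 fix the FAS. Optional wording also has an innocent reading: CBR is analysed on both the FAS and the per-protocol set, so the denominator does vary by population, and nowhere does the plan say that it will remove unknown responses from the FAS analysis. This stands in large part. A reader might infer that the SAP has adopted exclusion as an analysis option. The documents do not support that; they contain one sentence in conflict with several mandatory ones.

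A reader might also infer that leaving out 3 or 4 patients turns a failed group into a success. That holds only for a group exactly one short, only under the interval rule, and only at 46 and 33 patients.

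Nor can the dropout allowance be taken as the number of unknown responses. Under SAP 3.3.1.6 one stable-disease assessment more than 6 weeks after the start gives a best response of SD, and progression within 12 weeks gives PD. A patient who leaves after a stable week-8 scan is therefore not UNK.

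What the reply does not remove is the contradiction. SAP 3.3.1.3 follows a definition of responder based on confirmed PR or better, so it settles ORR more directly than CBR, and the sentence specific to CBR remains the permissive one.

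**Conclusion.** The contradiction is certain and concerns the primary endpoint; its effect on the conclusion is conditional. If the permissive sentence were applied to the FAS analysis, 3 exclusions in Group 1 or 4 in Group 2 would carry a group that is one patient short past the interval criterion, while the count rule would still fail it. These figures assume the recruited sizes before any Phase I patients are added. Whether enough unknown responses will exist cannot be judged from the documents, and the 10% dropout allowance does not establish it. This should be corrected as an inconsistency on the primary denominator; it is not evidence that the sponsor plans to exclude these patients.

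**What to change.** In SAP 3.5.2.2, 3.7.2.1 (ORR, DCR and CBR) and 3.7.2.2 (ORR), reword the clause so that patients with a best overall response of UNK are not responders and will be included in the denominator. Add one sentence: FAS-based CBR, ORR and DCR use every FAS patient in the analysed group as the denominator, including any Phase I RP2D patients added to the final analysis, and the per-protocol analysis uses every patient in the per-protocol set.

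This needs no new data and brings the clause into line with SAP 3.3.1.3 and Protocol 10.5.1. At the sizes for which the SAP gives a count (33, and about 44 to 46), the interval and count rules then agree. The cost is that the reported rates may be slightly lower than with unknown responses removed.
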